Efficacy data collected during the Maintenance Period after the point of escape will be summarized in stand-alone tables using treatment groups consisting of the (re-)randomized treatment before escape and the escape information:

- PBO/Esc CZP
- CZP 200mg Q2W/Esc CZP
- CZP 400mg Q2W/Esc CZP
- CZP 400mg Q4W/Esc CZP

or/and using the following Escape Maintenance Treatment Groups:

- Esc CZP 200mg Q2W
- Esc CZP 400mg Q2W
- All Esc CZP (only for safety data)

Safety Evaluations - Blinded Maintenance Period:

Safety data of the Maintenance Period will be summarized by the following blinded treatment groups (include data only until escape if subject escapes; escape visit date inclusive unless it is an injection site reaction).

- PBO
- CZP 200mg Q2W
- CZP 400mg Q4W
- CZP 200mg Q2W + CZP 400mg Q4W
- CZP 400mg Q2W
- All CZP

Safety Evaluations - Escape Arms:

For those subjects who moved to the Escape Arm during Maintenance Period, safety data after the escape visit will be presented by the following escape maintenance treatment groups:

- Esc CZP 200mg Q2W
- Esc CZP 400mg Q2W
- All Esc CZP (only for safety data)

Combined Initial and Maintenance Period – Week 0 to Week 52

Selected efficacy data for the combined Initial and Maintenance Period will be summarized by randomized treatment group and maintenance treatment group.

Selected safety data for the combined Initial and Maintenance Period will be summarized using two different approaches. In the first approach, data will be summarized by the following blinded treatment groups (including data only until escape if subject escapes; escape visit date inclusive unless it is an injection site reaction):

- PBO
- CZP 200mg Q2W
- CZP 400mg Q4W
- CZP 200mg Q2W + CZP 400mg Q4W
- CZP 400mg Q2W

- All CZP

In the second approach, data will be summarized by the following treatment groups and regardless of whether the dose was administered as blinded or open-label treatment.

- PBO
- CZP 200mg Q2W
- CZP 400mg Q4W
- CZP 200mg Q2W + CZP 400mg Q4W
- CZP 400mg Q2W
- All CZP

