10.2 Adverse events

Definitions and Data Handling Conventions

AEs recorded on the Baseline day will be regarded as ‘treatment emergent’. AEs occurring either before study drug administration (pre-treatment) or more than 70 days after last study drug administration will not be considered to be treatment emergent (TEAE). If a subject dies during the treatment period (timeframe: first study drug administration to last study drug administration +70 days), then the period for TEAEs will end with the death date. If a subject

has a Safety follow-up visit that extends beyond 70 days after the last study drug administration, then the period for TEAEs for that subject will end at the last study drug administration + 70 days.

Non treatment emergent AEs will only be listed separately.

Only AEs occurred at or prior to the visit of Week 24 will be included in the interim analysis.

Adverse events that occur on the Week 16 visit date will be attributed to the initial randomized treatment. The only exception to this definition is for the following types of events:

- Those which code to a HLT of “Injection Site Reactions”
- Those which have been designated as an Injection Reaction on the AE CRF and do not code to an SOC of “Investigations”
- Those which have been identified as a hypersensitivity reaction or an anaphylactic reaction

When any of these events occur on the Week 16 visit date, the AE will be attributed to the treatment received at Week 16.

In general, AEs will be allocated to the treatment group based on the dose most recently received.

The following rules will be applied to impute partial onset dates for AEs:

If the AE onset date is completely unknown, then use the date of first dose in the Initial Period.

If only the year is specified:

If the year of first dose in the Initial Period is the same as the year of onset, then use the date of first dose in the Initial Period.

If the year of first dose in the Initial Period is not the same as the year of onset, then use January 1 of the year of onset.

If only the month and year are specified:

If the month and year of first dose in the Initial Period is the same as the month and year of onset, then use the date of first dose in the Initial Period.

If the month and year of onset is after the month and year of first dose in the Initial Period and prior to the month and year of first dose in the Maintenance Period, then use the 1st of the month.

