- Demyelinating-like disorders. These will be presented in a stand-alone table which is based on the SMQ = “Demyelination”. The SMQ search should include all TEAEs which code to a PT included in Scope=Narrow group within the SMQ. TEAEs which code to a PT included in the Scope=Broad group within the SMQ should be excluded from the search.
- Aplastic anemia, pancytopenia, thrombocytopenia, neutropenia, and leucopenia. These will be presented in a table using the criteria SMQ = “Haematopoietic cytopenias (SMQ)” in the subset of SAEs. The SMQ search will include terms in the Scope=Narrow and Scope=Broad groups.
- Serious bleeding events. These will be presented in a table using the criteria SMQ = “Haemorrhage terms (excl laboratory terms) (SMQ)” in the subset of SAEs.
- Lupus and lupus-like illness. These will be manually identified by the study physician from the previously described Any TEAE table. No separate table is planned.
- Serious skin reactions (eg, Stevens-Johnson Syndrome, toxic epidermal necrosis, and erythema multiforme). These will be manually identified by the study physician from the previously described Any SAE table. No separate table is planned.

The tables for the AEOIs will include the incidence rate with associated 95% confidence interval, and the exposure adjusted event rate.

Will also be summarized:

- Hepatic events. They will be identified using the following 5 SMQs: “Cholestasis and jaundice of hepatic origin (SMQ)”; “Hepatic failure, fibrosis and cirrhosis and other liver damage-related conditions (SMQ)”; “Hepatitis, noninfectious (SMQ)”; “Liver-related investigations, signs and symptoms (SMQ)”; and “Liver-related coagulation and bleeding disturbances (SMQ)”.
- Hypersensitivity reactions and anaphylactic reactions. Hypersensitivity reactions will be identified as TEAEs that emerge on the same day or within one day after a study medication injection reaction was received which code to the following 10 PTs: “Administration site hypersensitivity”; “Documented hypersensitivity to administered product”; “Drug hypersensitivity”; “Hypersensitivity”; “Hypersensitivity vasculitis”; “Infusion site hypersensitivity”; “Injection site hypersensitivity”; “Medical device

hypersensitivity”; “Type II hypersensitivity”; “Type IV hypersensitivity reaction”. Anaphylactic reactions will be identified using UCB-defined search criteria.

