- Major Cardiovascular Events (MACEs). They will be identified using the following SMQs: “Central nervous system haemorrhages and cerebrovascular conditions (SMQ)”, which includes the 3 following sub SMQs: “Conditions associated with central nervous system haemorrhages and cerebrovascular accidents (SMQ)”, “Haemorrhagic central nervous system vascular conditions (SMQ)”, “Ischaemic central nervous system vascular conditions (SMQ)” except events coding to PT “Transient ischaemic attack”. All serious TEAEs which code to a PT included in the HLT “Ischaemic coronary artery disorders” except events coding to PT “Chest Pain” or “Chest discomfort” and all serious TEAEs which code to a PT included in any of the following HLTs: “Heart Failures NEC”, “Left Ventricular Failures”, or “Right Ventricular Failures” and which also code to the SOC of “Cardiac Disorders” as Primary SOC will be included.

AE Summaries by Period

All of the presentations described above will be presented for the Initial Period. Subsets of the presentations described above will be presented for the Maintenance Period and for the Combined Initial and Maintenance Period. Details for these summaries are described below.

Initial Period

Summaries for the Initial Period will be presented by randomized treatment group (PBO, CZP 200mg Q2W, CZP 400mg Q2W, All CZP) based on the SS, PsA Set and the CSS. For these summaries, treatment-emergence is defined as follows:

- For subjects who complete the Week 16 visit and continue to the Maintenance Period, all AEs which started on or after the date of first dose of study medication and on or prior to the date of the Week 16 administration of study medication will be considered a TEAE for these summaries. The only exception to this rule is for the following types of events:
 - Those which code to a HLT of “Injection Site Reactions”
 - Those which have been designated as an Injection Reaction on the AE CRF and do not code to an SOC of “Investigations”
 - Those which have been identified as a hypersensitivity reaction or an anaphylactic reaction

When any of these events occur on the date of treatment switch at Week 16, the AE will be attributed to the treatment initiated at Week 16.

- For subjects who discontinue on or prior to the Week 16 visit, all AEs which started on or after the first dose of study medication and on or prior to the date of last administration of study medication + 70 days will be considered a TEAE for the analysis summaries.

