^e Includes evaluation of signs and symptoms of active TB and risk for exposure to TB.

^f Screening chest x-ray must have been performed within 3 months prior to the Screening Visit.

^g PASI, PGA, and BSA will not be performed for subjects with generalized pustular PSO. The Global Improvement Score, JDA Severity Index, and CGI-I will be performed for subjects with generalized pustular PSO. For subjects with erythrodermic PSO, the CGI-I will be performed. Note: The CGI-I and Global Improvement Score will not be performed at Screening or Baseline.

^h For subjects with psoriatic nail disease only

ⁱ For subjects with PsA: HAQ-DI, Patient's Assessment of Arthritis Pain (VAS), and PGADA (VAS)

^j For subjects with PsA: swollen and tender joint counts and PhGADA (VAS)

^k Adverse events should be reported only if they occur after signing the Informed Consent form.

^l IMP administration of the IMP will occur after all other visit assessments have been completed.

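### SAP 3.6.1 and 10.2 conflict on injection-related reactions dated on the escape visit; for escapes at Week 24, 32 or 40, SAP 3.6.1 counts a same-day reaction to a placebo subject's first CZP dose as a placebo event

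*SAP*

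**What the plan says.** **SAP 3.6.1.** For blinded-treatment safety summaries, data count until escape, "escape visit date inclusive unless it is an injection site reaction". The condition appears twice: for the Blinded Maintenance Period and for the first approach to the Combined Initial and Maintenance Period. For the escape arm, "safety data after the escape visit will be presented by the following escape maintenance treatment groups".

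**SAP 10.2, definitions.** Events on the Week 16 visit date belong to the initially randomized treatment, with three exceptions: the injection site reaction HLT; events designated on the CRF as injection reactions (unless coded to the Investigations SOC); and a third group, "Those which have been identified as a hypersensitivity reaction or an anaphylactic reaction". For these, "When any of these events occur on the Week 16 visit date, the AE will be attributed to the treatment received at Week 16". The Initial Period part of 10.2 repeats the list and the rule: "When any of these events occur on the date of treatment switch at Week 16, the AE will be attributed to the treatment initiated at" that visit. Neither place mentions Week 24, 32 or 40.

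**SAP 10.2, general rule.** "In general, AEs will be allocated to the treatment group based on the dose most recently received". SAP 3.6 likewise bases safety analyses on actual treatment.

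**Timing.** SAP 2.3.1.3 allows escape at Week 16, 24, 32 or 40, and Protocol 5.1.1.3 starts open-label CZP at the visit where the PASI50 criterion is missed. At each visit the injection comes last: "IMP administration of the IMP will occur after all other visit assessments have been completed" (SAP Table 13-1, footnote l).

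**The concern.** Keeping ordinary escape-day events with the previous treatment is sensible, because assessments precede the injection. Acute reactions to the injection are different. SAP 10.2 itself ties hypersensitivity to the dose just given: "Hypersensitivity reactions will be identified as TEAEs that emerge on the same day or within one day after a study" medication injection. At an escape visit, that dose is open-label CZP, and for a placebo subject it is the first CZP received in the study.

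The exception in 3.6.1 covers only injection site reactions. An anaphylactic or hypersensitivity reaction hours after a first CZP dose would therefore appear in the placebo column of a blinded-only table, and could be missing from the escape tables. Two programmers, one working from 3.6.1 and the other from 10.2, would produce different tables from the same data.

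**Working it through.** The plan states no figure to reproduce. The check sets the rules side by side for one case: a placebo subject has a hypersensitivity or anaphylactic reaction on the day of the first escape CZP dose.

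| Escape visit | SAP 3.6.1 | SAP 10.2, exception list | SAP 10.2, general rule | Outcome |
|---|---|---|---|---|
| Week 16 | Placebo | Escape CZP | Not needed | Contradiction; the specific 10.2 rule gives CZP |
| Week 24, 32 or 40 | Placebo | Silent | Escape CZP | Unresolved; the only rule written for the escape date gives placebo |

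No text says which section prevails.

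**Numerator against denominator.** In SAP 10.1.2 (Combined Period, blinded treatment only), the time at risk of a subject who does not switch at Week 16 and escapes later is:

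days at risk = date of first open-label dose − date of first blinded dose, with no added day.

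Take an escape exactly at Week 24. The difference is 24 × 7 = 168 days, which covers study days 1 to 168. The open-label dose falls on day 169, outside the blinded time at risk. SAP 3.6.1 nevertheless places the day-169 reaction in the blinded numerator. This matters because the TEAE and serious TEAE tables in the blinded-only set carry exposure-adjusted rates.

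**Which outputs are exposed.**
- SAP 10.2 lists four blinded-only Combined Period tables for the Safety Set and PsA Set: overview, TEAEs, serious TEAEs, and TEAEs leading to permanent discontinuation. These are directly exposed.
- The open-label Maintenance Period tables may be exposed. SAP 3.6.1 admits only data after the escape visit, which drops the event. SAP 10.2 defines these tables by events arising on escape treatment, which would include it. Depending on the reading, the event is lost from the escape tables or appears there as well as under placebo in the blinded-only tables.
- The second Combined Period approach (blinded plus open-label) has no escape-date clause, so the general rule applies and gives CZP.
- Next-day reactions fall after the escape date under either section and are unaffected.

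**Size.** The planned placebo arm is 25 (Protocol 14.8.1). One misattributed subject changes the placebo incidence by 1/25 = 4.0 percentage points. The number of placebo subjects escaping at Week 24, 32 or 40 is not given. SAP 8 says only that most placebo subjects switch at or after Week 16, with no split by visit.

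**The case against.** The strongest reply is that 3.6.1 is a general grouping note for all safety data, whereas 10.2 is the dedicated adverse event section and should govern. Its general rule and the actual-treatment principle in SAP 3.6 both point to CZP, so an experienced programmer might well reach the right answer. This has force, but it does not settle Weeks 24, 32 and 40: the 3.6.1 condition is the only rule written for the escape date, and the 10.2 rule is introduced as applying in general.

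Three stronger readings are tempting, and the documents do not support them.

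- *A reader might infer that every placebo escaper is affected.* Week 16 escapes are explicitly covered by the 10.2 exception, stated twice. Only later escapes lack a rule of that kind.
- *A reader might infer that the CZP-versus-placebo comparison of hypersensitivity is biased throughout, or that a small blinded-maintenance placebo group would magnify one event.* The Initial Period presentations, which include the hypersensitivity summary, use the wider exception. The tables of AEs of interest for the Combined Period are listed in the blinded-or-open-label set, and the blinded-only set has no dedicated hypersensitivity table. SAP 10.2 lists Maintenance Period AE tables for escape treatment only, so a larger percentage for blinded maintenance would have no listed table behind it.
- *A reader might infer that the partial-date rules compound the problem and need changing.* For the excepted event types, an onset imputed to the Week 16 dose date goes to the Week 16 treatment, not the initial arm. Imputing every day-missing onset in a switch month to the switch date, and assigning it to the new treatment, would move genuine pre-switch events into CZP.

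It is also fair to note that the same-day or next-day definition applies to hypersensitivity; anaphylactic reactions are found by sponsor-defined search criteria.

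**Conclusion.** The conflict is real and should be corrected. At Week 16 it is a contradiction in wording that the specific 10.2 rule resolves correctly. At Weeks 24, 32 and 40, the text of 3.6.1 assigns a same-day hypersensitivity or anaphylactic reaction to the placebo arm although CZP was injected, and nothing in the plan overrides it clearly. CRF-designated injection reactions that are not injection site reactions fall in the same gap.

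The consequence is limited: rows and counts in four general blinded-only tables, and possibly the escape tables. The 4-point figure assumes one such event and the planned 25 placebo subjects. It is not a forecast, because the documents give neither the number of late placebo escapers nor an event rate. The efficacy analyses are not touched.

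**What to change.** - In both places in SAP 3.6.1, replace the injection-site-reaction condition with the three-category exception of SAP 10.2.
- In SAP 10.2, extend that exception from the Week 16 date to every escape visit (Weeks 16, 24, 32 and 40), so that these events go to the treatment injected at that visit.
- Make the escape-arm sentence in 3.6.1 consistent, so that excepted events on the escape date enter the escape tables.
- Leave other escape-date events with the blinded arm, and leave the partial-date imputation as it is.

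The cost is SAP wording and one programming condition. No new data are needed.

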3.6.2 Subjects with erythrodermic PSO or generalized pustular PSO

Period 2 – Initial Period - Week 0 to Week 16

Efficacy and Safety Evaluations:

Efficacy and Safety data will be presented by the following randomized treatment groups:

- Erythrodermic PSO CZP 200mg Q2W
- Erythrodermic PSO CZP 400mg Q2W
- Erythrodermic PSO All CZP (only for safety data)
- Generalized Pustular PSO CZP 200mg Q2W
- Generalized Pustular PSO CZP 400mg Q2W
- Generalized Pustular PSO All CZP (only for safety data)
- All Subjects (only for safety data)

Selected parameters (where stated in the following sections) may be summarized by treatment group and subgroup (Definition of subgroups, see [Section 4.8](#)).

Period 3 – Maintenance Period - Week 16 to Week 52

Efficacy Evaluations:

During the 36-week Period 3, subjects will be allocated to dose groups based on their Week 16 PASI50 response/Global Improvement Score, as appropriate based on PSO type, and whether or not the subject ever up-titrated their dose during the Maintenance Period. Efficacy data will be summarized based on the following maintenance treatment groups:

- Erythrodermic PSO CZP 200mg Q2W/CZP 200mg Q2W – includes subjects who remained on CZP 200mg Q2W for the duration of both periods
- Erythrodermic PSO CZP 400mg Q2W/CZP 400mg Q2W – includes subjects who remained on CZP 400mg Q2W for the duration of both periods
- Erythrodermic PSO CZP 200mg Q2W/CZP 400mg Q2W – includes subjects who up-titrated to CZP 400mg Q2W at any point during the Maintenance Period
- Generalized Pustular PSO CZP 200mg Q2W/CZP 200mg Q2W – includes subjects who remained on CZP 200mg Q2W for the duration of both periods

- Generalized Pustular PSO CZP 400mg Q2W/CZP 400mg Q2W – includes subjects who remained on CZP 400mg Q2W for the duration of both periods
- Generalized Pustular PSO CZP 200mg Q2W/CZP 400mg Q2W – includes subjects who up-titrated to CZP 400mg Q2W at any point during the Maintenance Period

Safety Evaluations:

For safety analysis, data of the Combined Initial and Maintenance Period will be summarized using the same treatment groups as listed for the Initial Period. Additionally, all Generalized Pustular PSO, all Erythrodermic PSO and all subjects will be summarized.

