3.6 Treatment assignment and treatment groups

All safety analyses and pharmacokinetic analyses will be based on actual treatment assignment, whereas all efficacy analyses will be based on randomized treatment assignment, unless specified otherwise. Analyses for escapers will be based on Escape Maintenance Treatment Group or on the latest dose of study medication the subject received before escape.

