For subjects who die, this calculation reverts to date of death – date of first administration of open-label CZP 400mg Q2W study medication + 1 day.

- If the subject was not initially randomized to CZP 200mg Q2W or CZP 400mg Q2W and discontinues prior to the Week 52 visit:
 - Date of Week 16 administration of study medication – date of Week 0 administration of study medication is attributed to the original treatment
 - Date of first administration of open-label CZP 400mg Q2W study medication – date of first administration of open-label CZP 200mg Q2W study medication is attributable to CZP 200mg Q2W.
 - For CZP 400mg Q2W, use the minimum of the following:
 - (1) Date of last administration of open-label CZP 400mg Q2W study medication – date of first administration of open-label CZP 400mg Q2W study medication + 70 days
 - (2) Date of last clinical contact – date of first administration of open-label CZP 400mg Q2W study medication + 1 day

For subjects who die, this calculation reverts to date of death – date of first administration of open-label CZP 400mg Q2W study medication + 1 day.

Combined Initial and Maintenance Period

Cohort subjects

Duration of exposure

For subjects who discontinue on/prior to the Week 16 visit:

- Date of last administration of study medication – date of first administration of study medication + 14 days

For subjects who die, if date of last administration of study medication + 14 days extends to a date beyond the date of death, then this calculation reverts to date of death – date of first administration of study medication + 1 day

For subjects who do not up-titrate to CZP 400mg Q2W at Week 16 or at any point during Maintenance:

- Date of last administration of study medication – date of first administration of study medication + 14 days

For subjects who die, if date of last administration of study medication + 14 days extends to a date beyond the date of death, then this calculation reverts to date of death – date of first administration of study medication + 1 day.

For subjects who do up-titrate to CZP 400mg Q2W during Maintenance:

- Date of first administration of CZP 400mg Q2W study medication – date of first administration of CZP 200mg Q2W study medication is attributable to CZP 200mg Q2W.
- Date of last administration of CZP 400mg Q2W study medication – date of first administration of CZP 400mg Q2W study medication + 14 days is attributable to CZP 400mg Q2W.

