For subjects who die, this calculation reverts to date of death – date of first administration of study medication + 1 day

For subjects who do up-titrate to CZP 400mg Q2W during Maintenance:

- Subjects who complete the Week 52 visit:
 - Date of first administration of open-label CZP 400mg Q2W study medication – date of first administration of open-label CZP 200mg Q2W study medication is attributable to CZP 200mg Q2W.
 - Date of last administration of open-label CZP 400mg Q2W study medication – date of first administration of open-label CZP 200mg Q2W study medication + 70 days is attributable to CZP 400mg Q2W.

For subjects who die, this calculation reverts to date of death – date of first administration of open-label CZP 400mg Q2W study medication + 1 day.

- Subjects who discontinue prior to the Week 52 visit:
 - Date of first administration of open-label CZP 400mg Q2W study medication – date of first administration of open-label CZP 200mg Q2W study medication is attributable to CZP 200mg Q2W.
 - For CZP 400mg Q2W time at risk, use the minimum of the following:
 - (1) Date of last administration of open-label CZP 400mg Q2W study medication – date of first administration of open-label CZP 400mg Q2W study medication + 70 days
 - (2) Date of last clinical contact – date of first administration of open-label CZP 400mg Q2W study medication + 1 day

For subjects who die, this calculation reverts to date of death – date of first administration of open-label CZP 400mg Q2W study medication + 1 day.

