If the month and year of first dose in the Maintenance Period is the same as the month and year of onset, then use the date of first dose in the Maintenance Period.

If the month and year of onset is after the month and year of first dose in the Maintenance Period, then use the 1st of the month.

If the intensity of an adverse event is unknown, it is considered as severe.

If the relationship to study drug is missing, it is considered as related.

Subject time at risk represents the time a subject was at risk for having an AE. The definitions for subject time at risk (in days) for the Initial Period, Maintenance Period, and Combined Initial and Maintenance Period are outlined in [Section 10.1](#). These definitions will be used for

exposure-adjusted AE summaries. Selected AE summaries will include the exposure adjusted incidence rate (EAIR) with associated 95% confidence interval and the exposure adjusted event rate (EAER).

For EAIR, the numerator will be the total number of subjects experiencing the AE. The denominator will be 100 subject-years; that is, the total summation of individual subject-years at risk up to the first occurrence of the AE for subjects with that AE, and the total subject-years at risk for those subjects not experiencing that AE, divided by 100. EAIRs will be presented with a 95% exact confidence interval based upon the Chi-Square distribution (Ulm, 1990).

For EAERs, the numerator will be the number of AEs including repeat occurrences in individual subjects; the denominator will be 100 subject-years. That is, the total summation of individual subject-years at risk divided by 100. No confidence interval will be computed for EAER.

Presentation Conventions

The frequency of all TEAEs during the study period will be presented by treatment group and period separately by SOC, High Level Term (HLT), and preferred term (PT). The data will be displayed as number of subjects experiencing the AE, percentage of subjects, and number of AEs, sorted by descending frequencies of PTs in the 'All CZP Subjects' column and ordered alphabetically for SOC, HLT and identical frequencies for PTs.

Tables for the Incidence of TEAEs – Overview and Incidence of TEAEs will be generated by TE-ADA status using the following categories:

1. TEAEs starting before 1st anti-CZP antibody positive
2. TEAE starting on or after 1st anti-CZP antibody positive
3. TEAEs for subjects who are always anti-CZP antibody negative

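### SAP 3.6.2 does not say whether cohort safety events after up-titration follow the randomised or the received dose, and SAP 10.1.2 divides time at risk by dose with a faulty formula for completers

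*SAP*

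**What the plan says.** SAP 3.6.2 introduces the cohort's Initial Period groups with "Efficacy and Safety data will be presented by the following randomized treatment groups" and lists 200mg Q2W and 400mg Q2W within each psoriasis type, plus pooled safety columns. For Period 3 it says that Combined Initial and Maintenance Period safety data are "summarized using the same treatment groups as listed for the Initial Period". The same section creates a separate 200mg-to-400mg group for efficacy, but none for safety.

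Three other places bear on the same subjects:

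- SAP 3.6: "All safety analyses and pharmacokinetic analyses will be based on actual treatment assignment". The sentence ends with an allowance for exceptions that are specified elsewhere.
- SAP 10.2: "In general, AEs will be allocated to the treatment group based on the dose most recently received". For the denominator of the exposure-adjusted rates it points to Section 10.1: "The definitions for subject time at risk (in days) for the Initial Period, Maintenance Period, and Combined Initial and Maintenance Period are outlined in".
- SAP 10.1.2, Combined Period, cohort subjects, has its own rules headed "For subjects who do up-titrate to CZP 400mg Q2W during Maintenance". Under these, time at risk on 200mg is "Date of first administration of open-label CZP 400mg Q2W study medication – date of first administration of open-label CZP 200mg Q2W study medication", and later time goes to 400mg.

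SAP 10.2 presents Initial Period adverse event tables by randomised treatment group. For the Combined Period, with the Cohort Safety Set (CSS) included, it changes to 'safety treatment group', a term it does not define for the CSS.

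**The concern.** An event rate is interpretable only if events and time at risk are assigned to columns by the same rule. Here one section points to the randomised dose for the columns, while another divides the same subject's time by dose received. Nothing reconciles them.

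A programmer who takes the columns and events from 3.6.2 and the time from 10.1.2 would put events that occur on 400mg over a denominator that stops at the end of 200mg treatment. The 400mg column would gain time without the events that belong to it. Two doses with the same true rate would then appear to differ, with 200mg looking worse. The cohort is small, so a single up-titrated subject is enough to show this. The open-label Maintenance Period adverse event tables in SAP 10.2 use the Safety Set and the PsA Set only, so no separate cohort table would reveal the problem.

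**Working it through.** The plan gives no figure to reproduce. Protocol 14.8.2 states no sample-size calculation for this cohort, and these rates are descriptive. The check is day-count arithmetic on the SAP 10.1.2 formulas.

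**Inputs from the documents**
- At least 5 subjects per dose (SAP 2.3.2.2); 5 is used.
- Up-titration from 200mg to 400mg is possible from Week 16 (SAP 2.3.2.3).
- Time at risk for a completer who does not up-titrate: Week 50 dose date minus first dose date, plus 70 days (SAP 10.1.2).

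**Assumptions, not in the documents**
- k = 1, 2 or 3 of the 5 subjects on 200mg up-titrate at Week 16.
- All subjects complete on schedule.
- The true event rate is constant and the same on both doses.
- Psoriasis types are pooled.

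**One subject**
- No up-titration: 50 × 7 + 70 = 420 days = 60 weeks.
- Up-titration at Week 16, time on 200mg: 16 × 7 = 112 days = 16 weeks.
- Time on 400mg with a clean split (from the first 400mg dose): 350 − 112 + 70 = 308 days = 44 weeks. Check: 112 + 308 = 420.
- Time on 400mg as printed for completers (last 400mg dose minus first **200mg** dose, plus 70 days): 350 + 70 = 420 days = 60 weeks. The total is then 112 + 420 = 532 days for a 420-day span. The formula for discontinuers starts at the first 400mg dose and does not have this fault.

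**Column totals if events follow randomised dose and time follows dose received**

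Each column holds the events from 5 × 60 = 300 subject-weeks, so the bias factor is 300 divided by the column's time.
- 200mg time = (5 − k) × 60 + k × 16
- 400mg time, clean split = 300 + k × 44
- 400mg time, as printed = 300 + k × 60

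| k | 200mg | 400mg, clean split | 400mg, as printed |
|---|---|---|---|
| 1 | 300/256 = 1.17 | 300/344 = 0.87 | 300/360 = 0.83 |
| 2 | 300/212 = 1.42 | 300/388 = 0.77 | 300/420 = 0.71 |
| 3 | 300/168 = 1.79 | 300/432 = 0.69 | 300/480 = 0.625 |

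Later up-titration weakens the effect under a clean split. With 1 of 5 at Week 40, the 200mg factor is 300/280 = 1.07 and the 400mg factor is 300/320 = 0.94.

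**Events counted by dose received, printed formula kept**

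The 200mg rate is then correct, but the 400mg rate is still too low: 344/360 = 0.96, 388/420 = 0.92 and 432/480 = 0.90 for k = 1, 2 and 3.

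**One rule for both events and time, with the formula corrected**

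The factor is 1.00 in both columns.

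**The case against.** The strongest reply is that nothing need be mixed. No sentence says that an up-titrated subject's events stay in the 200mg column to Week 52. The word 'randomized' stands in the Initial Period paragraph, where it does no harm because up-titration starts only at Week 16. The Period 3 sentence may mean only that the same column labels are reused. On that reading, SAP 3.6, 10.2 and 10.1.2 all attribute by dose received, and the change of term in 10.2 from randomised to safety treatment group supports it. Alternatively, if 3.6.2 governed both events and time, the rates would be consistent by randomised arm.

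This stands in part: a reader might infer that the SAP makes mixed rates inevitable, and it does not. But the label reading is nowhere stated. SAP 3.6 and 10.2 both yield to more specific text, and 3.6.2 is specific on grouping while 10.1.2 is equally specific on time. Two programmers could produce different tables.

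Three further inferences go too far:
- These are not the only dose-specific safety rates for the cohort. SAP 10.2 also plans Initial Period EAIR and EAER for the CSS, before any up-titration.
- The percentages apply to EAER. The exposure-adjusted incidence rate (EAIR) counts subjects and stops time at the first occurrence, so its distortion would differ.
- Simply aligning 3.6.2 to 10.1.2 is not sufficient, because the printed completer formula does not divide time cleanly.

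It is also fair to say that columns split by psoriasis type hold only a few subjects, so these rates are imprecise under any rule.

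**Conclusion.** The SAP leaves the attribution of Combined Period cohort safety data unresolved for subjects who up-titrate. If 3.6.2 is applied to events and 10.1.2 to time, the 200mg EAER is overstated by 17% to 79%. The 400mg EAER is understated by 13% to 31% with a clean time split, or by about 17% to 38% with the formula as printed. These ranges rest on the stated assumptions, above all the number and timing of up-titrations, which the documents do not give.

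The completer formula in 10.1.2 is an error under any reading. It counts the 200mg period twice and lowers the 400mg rate by 4% to 10% in the same scenarios, even when events are counted by dose received.

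The consequence is confined to descriptive dose-specific rates in an exploratory cohort. Initial Period rates, event counts for all subjects together, and every hypothesis test are unaffected. The point is worth correcting because an apparent dose difference could arise from bookkeeping alone.

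**What to change.** Three wording changes in the SAP:

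1. In 3.6.2 (Period 3, Safety Evaluations), state that Combined Period cohort safety data are grouped by the dose received at event onset (CZP 200mg Q2W, CZP 400mg Q2W, All CZP, within psoriasis type), and that time at risk is attributed to the same dose.
2. In 10.2, define 'safety treatment group' for the CSS in the same terms.
3. In 10.1.2 (Combined Period, cohort subjects who up-titrate and complete Week 52), start 400mg time at risk at the first 400mg administration, as the formula for discontinuers already does.

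The cost is SAP text and matching table programs, with no new data. The downside is that up-titrated subjects appear in two dose columns, so the column Ns add to more than the total. A table footnote should say so.
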